2. SYNOPSIS

Trial Title	Investigation of Appropriate Timing of Additional Insulin Dosing for Fat and Protein in Children with Type 1 Diabetes using Multiple Daily Injections	
Internal ref. no. (or short title)	Fat/Protein Study	
Clinical Phase	Phase 4	
Trial Design	Controlled observational study	
Trial Participants	Children aged 6 to under 18 years of age with type 1 diabetes (T1DM)	
Planned Sample Size	40	
Treatment duration	1 week	
Follow up duration	No follow-up at the end of the trial period	
Planned Trial Period	1 year	
	Objectives	Outcome Measures
Primary	To determine whether additional insulin boluses for the fat and protein content of a meal given before, one or two hours after a meal optimise post-prandial blood glucose levels in children with Type 1 diabetes using multiple daily injections?	Continuous subcutaneous glucose profiles will be examined to determine – 
 • mean post-prandial glucose excursion for 8 hours following the test meal
Secondary	To examine other indices of BG control following additional insulin boluses for the fat and protein content of a meal given before, one or two hours after a meal in children with Type 1 diabetes using multiple daily injections?	Continuous subcutaneous glucose profiles will be examined to determine – 
 • peak BG level • peak BG excursion from baseline (pre-meal BG level) • time of peak BG level from baseline measurement • Rate of BG excursion from baseline to peak • mean post-prandial glucose excursion for 5 and 12 hours following the test meal • area under the curve at time-points 0-3 hours, 3-5 hours, 5-8 hours, 8-12 hours post-meal • Time from baseline BG at which BG returns to baseline level
Investigational Medicinal Product(s)	Insulin	
Formulation, Dose, Route of Administration	Insulin Aspart (NovoRapid) given in a dose according to the protocol, subcutaneously	

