Participants will be asked not to give a correction dose before the meal if the BG level is between 7-12mmol/l as this would interfere with the analysis. They will be asked, if possible, not to carry out the test meals if their pre-meal BG is greater than 12 mmol/l. But if they have to do the test meal with a high pre-meal BG (above 12 mmol/l) they will be instructed to give their usual correction bolus in addition to the prescribed insulin dose for the test meal. This data will be analysed separately. If BG is below 4mmol/l (hypoglycaemic) or above 16mmol/l participants will be asked to abandon the study evening and repeat on another evening. Full written instructions will be provided to the family for all aspects of the insulin dosing for the study meals.

During the study on the standardised meal days children will be instructed not to eat any food after the meal during the evening, and not to correct any later BG levels unless they are dangerously high (BG over 16 mmol/l with ketones over 0.5 mmol/l). If BG levels go low at any time (BG less than 4 mmol/l) children will be instructed to treat the hypoglycaemia according to their usual management, and omit

any further study doses of insulin if the hypoglycaemia occurs after a first study dose and a second is due. This data will be analysed separately. Children and families will be asked to complete diaries during the trial week.

At the end of the study period (the day after the third meal), children will come back to the research facility or clinic for the end of study visit (visit 3). A research nurse or dietitian will remove the CGM sensor and download the data onto a secure laptop. Children and their families will then be asked to complete a short questionnaire about the acceptability of using the extra insulin doses, and their perceptions as to whether there were any beneficial or adverse effects.

The study dietitian will calculate standard outcomes from each patient's sensor download and pass on anonymously to the study statistician to analyse the data.

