11.1. Description of Statistical Methods

Descriptive statistics will be used to describe the group demographics and outcomes.

The continuous glucose records will be analysed methodically by the CI, research dietitian and statistician. Data to be obtained include –

- pre-meal BG level
- peak BG level
- peak BG excursion from baseline at 3, 5, 8 and 12 hours following the meal
- time of peak BG level
- time of peak BG excursion
- area under the curve at time-points 0-4 hours, 4-6 hours, 6-8 hours, 8-12 hours post-meal

The relationship between the insulin timing and the mean change in postprandial blood glucose levels will be analysed and described.

Comparisons using paired t tests for normally distributed data, and Mann-Whitney U tests for non-parametric data will be used to examine the differences in areas under the postprandial BG curves and the postprandial BG levels by insulin timing.

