11.2. The Number of Participants

We estimate that using a three-treatment, three period cross-over design, 36 people will achieve 80% power to detect a 2 mmol/L difference in mean 5 hour postprandial glucose excursion at the 5% significance level. Although we do not anticipate any losses to follow-up or withdrawals due to side-effects from the study we will aim to recruit 40 to ensure power is maintained if this does arise. This power calculation has been carried out by our study statistician.

In order to allow for drop-outs, we have made the decision to recruit 40 patients.

Previous intervention studies of fat/protein interventions in children using insulin pumps have used 24-42 patients with significant differences in BG levels at the 0.04 and 0.03 levels of significance (5-8).

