11.3. The Level of Statistical Significance

$P < 0.05$ will be used to demonstrate statistical significance.

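### Pre-meal glucose is recorded at every test meal but never used as a covariate, so the timing comparisons lose precision that could be recovered at almost no cost

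*Combined protocol and SAP*

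**What the plan says.** Section 6.3 sets the entry rule for a test meal. At the extremes, "If BG is below 4mmol/l (hypoglycaemic) or above 16mmol/l participants will be asked to abandon the study evening". In the middle, "Participants will be asked not to give a correction dose before the meal if the BG level is between 7-12mmol/l". No correction is called for between 4 and 7. A meal can therefore start uncorrected anywhere from 4 to 12 mmol/L, and nothing limits how far one child's three starting values may differ. Meals started above 12 receive a correction and are to be analysed separately.

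The outcomes treat the starting value in different ways:

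- Peak BG level is an absolute value.
- Peak excursion is taken from the pre-meal level (Sections 2 and 5). Mean excursion, the primary outcome at 8 hours, is naturally read the same way.
- AUC appears in the Synopsis as "area under the curve at time-points 0-3 hours, 3-5 hours, 5-8 hours, 8-12 hours post-meal" and in Section 11.1 with different windows. Neither place says total or incremental.

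Section 11.1 lists the pre-meal level among the data to be obtained. It then names paired t tests and Mann-Whitney U tests to "examine the differences in areas under the postprandial BG curves and the postprandial BG levels by insulin timing". Neither test takes a covariate, and Sections 11.2 to 11.7 add no model or adjustment.

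On size, Section 11.2 states that "36 people will achieve 80% power to detect a 2 mmol/L difference in mean 5 hour postprandial glucose excursion at the 5% significance level". No SD is given.

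**The concern.** Suppose a child starts one test meal at 5 and another at 11.5 mmol/L. Part of that gap will persist into the post-meal curve and part will fade. An absolute outcome keeps the persisting part as apparent response. An excursion removes the whole gap, including the part that would have faded anyway. Either way, variation in starting glucose that has nothing to do with insulin timing enters the comparison of timings.

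The two families of outcome absorb it with opposite signs. One chance imbalance can therefore push peak or total AUC towards one timing and excursion towards another. At stake are the precision of the primary comparison and the consistency of the secondary ones, in a trial of only 36 to 40 children.

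**Working it through.** **Inputs from the documents.** n = 36, 80% power, difference 2 mmol/L, 5% level (Sections 11.2 and 11.3; two-sided assumed); uncorrected starts of 4 to 12 mmol/L (Section 6.3).

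**Inputs assumed.** Within-child evening-to-evening SD of pre-meal glucose, s: 1.0 to 2.31 mmol/L, where 2.31 = 8/√12 is the SD of a uniform spread over 4 to 12. Slope of later glucose on pre-meal glucose within a child, b: 0 to 1. Neither is in the documents.

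**1. The plan's own figure.** With no SD stated, 36 can only be solved backwards. By the normal approximation, SD of the paired difference = 2 × √36 / (1.960 + 0.842) = 4.28. With the noncentral t on 35 df it is 4.165, a variance of 17.35. This applies to the 5-hour excursion named in Section 11.2; the primary outcome is the 8-hour one.

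**2. Chance imbalance in starting glucose between two timings.** The 95% range is ±1.96 × s × √(2/36).

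**3. How it enters the contrast.** If the mean start differs by D, an absolute outcome shifts by b × D and an excursion by −(1 − b) × D. The shift vanishes only at b = 0 for absolute values and b = 1 for excursions, so no single slope spares both.

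**4. Variance removed from the excursion comparison by adjustment.** Share = (1 − b)² × 2s² / 17.35.

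| s | Imbalance, 95% | Cut at b = 0.3 | Cut at b = 0.5 | Adjusted power at b = 0.5 |
|---|---|---|---|---|
| 1.0 | ±0.46 | 0.98/17.35 = 5.6% | 0.50/17.35 = 2.9% | 81.1% |
| 1.5 | ±0.69 | 2.205/17.35 = 12.7% | 1.125/17.35 = 6.5% | 82.5% |
| 2.0 | ±0.92 | 3.92/17.35 = 22.6% | 2.00/17.35 = 11.5% | 84.5% |
| 2.31 | ±1.07 | 5.23/17.35 = 30.1% | 2.67/17.35 = 15.4% | 86.1% |

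The last row is an extreme: it places the whole of a uniform 4-12 spread within each child and leaves none between children. The conclusions below use 1.0 to 2.0 for the variance cuts.

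**5. Dependence on b, at s = 2.0, n = 36, excursion analysis held at 80%.** The absolute column is for a mean level over the same window.

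| b | Power, absolute value unadjusted | Power, adjusted | n for 80%, adjusted |
|---|---|---|---|
| 0 | 97% | 97% | 21 |
| 0.25 | 89% | 90% | 28 |
| 0.5 | 80% | 84% | 33 |
| 0.75 | 71% | 81% | 36 |
| 1.0 | 64% | 80% | 37 |

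**6. Simulation check** (20,000 trials, s = 2.0, b = 0.5). Type I error was 4.9% for excursion, 4.7% for absolute and 4.8% for adjusted. Power was 80%, 80% and 84%.

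**7. Incremental AUC.** Net area above the pre-meal value equals mean excursion times window length. It is full subtraction again, so on its own it leaves the (1 − b) term in place.

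**The case against.** The strongest reply is that this concerns efficiency, not validity. Order is randomised within child, so variation in starting glucose is already part of the variance that the paired test estimates. The simulation bears this out, and the point stands. A reader might infer that the timing comparison is biased, the more so because families choose the evenings knowing the order (Sections 6.3 and 8.3). That route to systematic imbalance is conceivable, but nothing in the documents shows that starting glucose would differ by timing.

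The reply also says that starting glucose was considered. The run-in week aims to make high or low evening values less likely, families are advised to avoid unsuitable days, and Amendment 3 restricted corrections to protect the analysis of change from the pre-meal level. These steps may well make s smaller than 2.0, which is why lower values are shown. They do not equalise the starts, and they give the recorded value no role as a covariate.

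Three further readings go too far:

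- That AUC will be compared as a total. This rests on silence; the supportable point is that AUC is undefined.
- That adjustment saves 33% or 20% of the excursion variance at b = 0.3 or 0.5. Those figures need a per-meal residual SD of 2 with s = 2.0, at which the unadjusted analysis would already have 92% or 96% power, not the stated 80%.
- That a chance imbalance would move the 0-3 hour AUC by about 2.8 mmol·h/L (0.92 × 3). That requires b = 1, where the excursion analysis loses nothing; at b = 0.5 it halves to about 1.4.

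**Conclusion.** The point holds as a near-free gain in precision. The plan records each meal's starting glucose, allows it to range over 8 mmol/L without correction, and does not adjust for it.

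For the excursion, with the paired-difference SD set at the 4.2 implied by Section 11.2 and s of 1.0 to 2.0, adjustment removes about 6-23% of the variance at b = 0.3 and 3-12% at b = 0.5. At b = 0.5 power rises from 80% to about 81-84%. At b = 1 essentially nothing is gained or lost. Unadjusted absolute outcomes stand to lose more when b is high, so which family suffers more depends on b.

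All of these sizes rest on assumed values of s and b and on a two-sided test. The conclusion that type I error is sound rests on the randomised order. That absolute and excursion outcomes would actually favour different timings is a possibility when b lies between 0 and 1, not something the documents establish.

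**What to change.** In Section 11.1:

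- For mean excursion, peak and each AUC window, compare timings within child with that meal's own pre-meal glucose as a covariate. A simple form regresses the paired difference in outcome on the paired difference in pre-meal glucose and tests the intercept. The value is taken before that evening's study insulin, so that evening's timing cannot affect it.
- State whether AUC is total or incremental, and apply the covariate either way. Incremental AUC alone is not a substitute.
- Tabulate pre-meal glucose by timing.

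Section 6.3 analyses meals corrected above 12 mmol/L separately, while Section 11.6 exempts a correction dose at the evening meal from separate analysis. These must be reconciled, because they decide which starting values enter the main comparison.

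The cost is a few lines of text and one degree of freedom per comparison. No new data or participants are needed, and the covariate analysis requires no change to a clinical rule.

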11.2. The Number of Participants

We estimate that using a three-treatment, three period cross-over design, 36 people will achieve 80% power to detect a 2 mmol/L difference in mean 5 hour postprandial glucose excursion at the 5% significance level. Although we do not anticipate any losses to follow-up or withdrawals due to side-effects from the study we will aim to recruit 40 to ensure power is maintained if this does arise. This power calculation has been carried out by our study statistician.

In order to allow for drop-outs, we have made the decision to recruit 40 patients.

Previous intervention studies of fat/protein interventions in children using insulin pumps have used 24-42 patients with significant differences in BG levels at the 0.04 and 0.03 levels of significance (5-8).

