It is suggested that for high fat meals containing over 40g fat that insulin doses should initially be increased by 30-35% on the usual dose calculated using their ICR with the extra insulin given as a separate injection 1 hr after the meal. This dose should be monitored and increased according to individual response [9].

They also recommend that for meals containing 30g fat and 40g protein that the insulin dose calculated with usual insulin:carbohydrate ratios should be increased by 15-20% but do not suggest a delivery method for this extra insulin [9]. It should be noted that all these recommendations are intended for an adult population.

The review recognises gaps in knowledge and evidence base to support specific recommendations and algorithms to calculate insulin doses and delivery patterns according to the fat and protein content of meals. Furthermore, they identified significant inter-individual variability in post-prandial glycaemic response to high fat and protein meals which may be a confounding factor to research and meaningful conclusions in this area [9].

We therefore plan to investigate how to appropriately administer additional insulin for the fat and protein content of high protein and high fat meals to children on multiple daily injections (MDI) to improve BG levels up to 12 hours after a meal.

In line with our previous studies (3,4) and as indicated from a power calculation, we will recruit forty patients from the Oxfordshire Children's Diabetes Service aged from 6 to under 18 years and obtain full informed consent. There will be a run-in period of 7 days during which time the children's insulin to carbohydrate ratios will be optimised.

The children will then be asked to wear continuous subcutaneous glucose monitors (CGM) which are a well-recognised and validated method of monitoring BG levels over several days. The particular version we will use for this study lasts for 7 days.

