11.4. Criteria for the Termination of the Trial

We would only anticipate 10 episodes of severe hypoglycaemia in 340 patients per year. Therefore the likelihood of a severe hypo occurring during this study under normal circumstances would be very small. So if we assume there is no increase in risk then we would only expect to see 2 severe hypos in one of the two arms in 3 out of every 10,000 trials, for a single hypo in either arm this increases to about 1 in every 100 trials. Therefore we would terminate the trial if we had 2 severe hypos occurring on any arm of the trial.

11.5. Procedure for Accounting for Missing, Unused, and Spurious Data.

We will use boxplots to identify outlying, unusual or spurious data using pre-defined decision rules (e.g. upper or lower quartiles $\pm 1.5 \times \text{IQR}$). In the case of implausible or unlikely outcome data we will look back at CRF's to rule out data handling errors. If outliers cannot be resolved then we will exclude this particular result from the main analysis. We intend to use a complete case analysis but we will conduct a sensitivity analysis to assess the impact of any missing data using appropriate multiple imputation methods.

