11.6. Inclusion in Analysis

All data available from all participants will be used for the analyses. If a child has become hypoglycaemic (BG $< 4.0 \text{ mmol/l}$) during the profile period then subsequent data will be analysed separately. If any child has had to treat a high BG level with additional insulin (except for a correction dose at the evening meal), then subsequent profile data will be analysed separately. However in either instance, the data up to the event will be included in all analyses. The two other meals would still be eligible for the study analyses if there were no similar events.

If there have been any protocol breaches, such as further food during the evening after the main meal, then all the subsequent data will not be used in the analysis for that meal. Education of the participants and parents will be vital to ensure that such eventualities are rare.

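### The sample size is calculated for the 5-hour mean excursion, but the primary outcome is the 8-hour mean, for which no power is given

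*Combined protocol and SAP*

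**What the plan says.** - **Primary outcome.** The Synopsis and the table in Section 5 give one primary outcome: "mean post-prandial glucose excursion for 8 hours following the test meal".
- **Status of the 5-hour mean.** The Synopsis lists it among the secondary outcomes: "mean post-prandial glucose excursion for 5 and 12 hours following the test meal". The Section 5 secondary list leaves it out. In neither place is it primary.
- **Sample size.** Section 11.2 makes the plan's only power statement: "36 people will achieve 80% power to detect a 2 mmol/L difference in mean 5 hour postprandial glucose excursion", at the 5% level in a three-treatment, three-period crossover. It raises 36 to 40 to cover losses. No SD is given.
- **Recruitment target.** Section 4 relies on that calculation, alongside precedent from the group's earlier studies: "as indicated from a power calculation, we will recruit forty patients".
- **Analysis variables.** Section 11.1 lists "peak BG excursion from baseline at 3, 5, 8 and 12 hours following the meal" and AUCs for 0-4, 4-6, 6-8 and 8-12 hours. It also promises an analysis of the mean postprandial change, without a time window. It does not name the mean 8-hour excursion.
- **Incomplete profiles.** Section 11.5 says "We intend to use a complete case analysis", with multiple imputation as a sensitivity analysis. Under Section 11.6, if a child becomes hypoglycaemic "during the profile period then subsequent data will be analysed separately", and the same applies after a treated high. Section 11.6 adds: "However in either instance, the data up to the event will be included in all analyses".

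**The concern.** A power statement supports a trial only for the outcome, window and test to which it refers. Here the only one refers to an outcome that is not primary. Three inputs can change between a 5-hour and an 8-hour mean: the true difference between timings, its SD, and the number of children with a full profile.

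The window is unlikely to be a neutral choice. The trial compares times of giving extra insulin for fat and protein, and Section 4 reports that glucose after such meals had not returned to pre-meal values up to 6 hours later. What happens between 5 and 8 hours is part of the primary outcome but not of the sizing calculation.

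Section 11 does not settle which window is meant, because it never names the mean 8-hour excursion. At stake is whether a null result on the primary outcome could be interpreted, and whether 36 completers is a justified number for it.

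**Working it through.** **1. What 36 implies.** No SD is stated, so 36 cannot be reproduced forwards; it can only be solved backwards. Inputs from Section 11.2: n = 36, power 80%, difference 2 mmol/L, alpha 5%. Assumed: a two-sided paired t test (Section 11.1 plans paired t tests; sidedness is not stated).

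- Noncentral t, df = 35: 80% power needs difference/SD = 0.480.
- Implied SD of paired differences = 2 / 0.480, about 4.16 mmol/L.
- Other readings also fit 36: one-sided 5% implies 4.73; two-sided 5% split over three contrasts implies 3.56.
- 36 / (1 - 0.10) = 40 agrees with the recruitment target.

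The figure of 36 is thus neither confirmed nor refuted. The point is which outcome it belongs to.

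**2. When the 5-hour power carries over.** For a test whose power depends on difference/SD, at the same n, 8-hour power is also 80% only if

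(8-hour difference) / 2 = (8-hour SD) / (5-hour SD) = r.

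Let the difference between timings average 2 mmol/L over 0-5 h and L over 5-8 h. Then

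8-hour difference = (5 × 2 + 3 × L) / 8 = (10 + 3L) / 8,

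and setting this equal to 2r gives the break-even value L = (16r - 10) / 3.

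**3. Plausible values of r (assumed).** With k = late-segment SD / early-segment SD and rho the correlation between segments,

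r = sqrt[(5/8)² + (3/8)² k² + 2(5/8)(3/8) rho k].

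- k = 0 (no variability after 5 h): r = 0.625
- k = 1, rho = 0: r = 0.73
- k = 1, rho = 1: r = 1.0
- r = 1.2 needs k of at least (1.2 - 0.625) / 0.375 = 1.53

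**4. Power for the 8-hour mean** (n = 36, two-sided 5% paired t test, 5-hour SD 4.16; an illustration, not a bound):

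| L over 5-8 h | 8-hour difference | r = 0.625 | 0.73 | 0.8 | 1.0 | 1.2 |
|---|---|---|---|---|---|---|
| -1 | 0.875 | 50% | 39% | 33% | 23% | 17% |
| 0 | 1.25 | 80% | 67% | 59% | 42% | 31% |
| 2 | 2.0 | 99% | 97% | 94% | 80% | 65% |
| 3 | 2.375 | >99% | >99% | 99% | 91% | 79% |
| Break-even L (mmol/L) | | 0 | 0.55 | 0.93 | 2.0 | 3.07 |

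**5. Number of complete pairs.** At r = 1.0 and 2 mmol/L, 40 / 36 / 32 complete pairs give 84 / 80 / 75%. A profile cut between 5 and 8 hours yields a full 5-hour mean but not a full 8-hour mean. How often that will happen is not stated.

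**6. Whether Section 11.1 resolves the window.** The 8-hour mean can be built from the listed pre-meal level and the 0-4, 4-6 and 6-8 h AUCs. The 5-hour mean cannot be built from those AUCs, because 5 h falls inside the 4-6 h window, although the 5-minute CGM record would give it. Section 11.1 therefore neither confirms the 5-hour window nor names the 8-hour mean as primary.

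**The case against.** The mismatch itself is hard to dispute. The strongest reply is that nothing follows from it: no figure is shown to be wrong, and 8-hour power could exceed 80%. That stands, and it limits the conclusion, but the primary outcome still has no power statement.

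Other points on that side:

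- **The illustration is not a range.** It rests on one back-solved SD, on non-negative correlation between segments, and on chosen values of L. If the timings cross after 5 hours (L = -1), power is lower still. This is right, so the table shows sensitivity only.
- **The lost-profile argument is speculative.** Section 11.5 adds multiple imputation as a sensitivity analysis, and Section 11.6 keeps data up to an event. This also stands: the effect on the number of usable 8-hour pairs is unknown in size.
- **Section 11.1 does mention an analysis of mean change, and its list need not be exhaustive.** True, but no 8-hour window is attached to that mean.
- **The secondary label for the 5-hour mean comes from the Synopsis alone, and Section 4 also cites earlier studies for the number forty.** Both are correct. Neither makes the 5-hour mean primary or supplies power for 8 hours.

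**Conclusion.** The concern holds, and Section 11.2 is wrong as written: the only sample-size justification is attached to an outcome other than the primary one. This follows from the text alone and needs no assumption.

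The consequence for power cannot be fixed from the documents, which give no SD for either window and no target difference for 8 hours. Under the assumptions in the working, the 5-hour power carries over only if the 8-hour difference and SD change in the same proportion; modest departures move it well away from 80% in either direction. The trial is not shown to be underpowered, and 36 is not shown to be miscalculated. This should be fixed before the primary result is interpreted.

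**What to change.** 1. The sponsor confirms that 8 hours is the primary window.
2. Restate Section 11.2 for the mean 8-hour excursion: assumed SD and its source, test, sidedness, number of complete 8-hour pairs, and the power or detectable difference at 36 completers. Alternatively, justify with data why the 5-hour figure carries over.
3. If the 5-hour figure is kept, label it as referring to a secondary outcome, and list that outcome in Section 5 as well as in the Synopsis.
4. Name the mean 8-hour excursion as the primary analysis variable in Section 11.1.
5. As a separate, lesser point, reconcile the AUC windows in Section 11.1 (0-4, 4-6, 6-8, 8-12 h) with those in the Synopsis and Section 5 (0-3, 3-5, 5-8, 8-12 h).

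The cost is wording in Sections 5, 11.1 and 11.2 and one recalculation. The rewording itself needs no extra patients, but the restated power may prove less favourable. For example, at 2 mmol/L and an SD ratio of 1.2, 80% power would need about 51 completers under the assumptions above. The sponsor could then report the lower power or the larger detectable difference, or reconsider the number.
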